7. STUDY-WIDE NUMBER OF SUBJECTS*

N/A

8. STUDY-WIDE RECRUITMENT METHODS*

N/A

9. **STUDY TIMELINES***

The total duration of the study will be 2 years and six months (see table below). Focus group participants will attend one 2-hour focus group session. Pilot RCT participants will attend one 1.5-hour study session (with up to 1 hour of pre-session work to review the intervention). Primary analyses will be completed by Year 3, Quarter 2.

Study Timeline	YEAR: QUART ER:	1				2				3	
		1	2	3	4	1	2	3	4	1	2
A i m 1	Hiring, training, and CITI certification of 4 Deaf Community Advisors										
	IRB approval and clinicaltrials.gov registration										
	Focus group recruitment, enrollment, and data collection (n = 36)										
	Qualitative analysis of focus group data										
	Film production of new Sign Here training intervention										
A i m 2	Pilot RCT preparation, IRB modification approval, and clinicaltrials.gov modification approval										
	Pilot RCT rolling recruitment, enrollment, randomization, and data collection (n = 80; recruitment rate \approx 14 participants per month)										
	Final data analyses, report/paper writing, and R01 proposal preparation										

10. **STUDY ENDPOINTS***

Aim 1a Focus Groups

After viewing the *Sign Here* prototype film, focus group participants will provide qualitative

INVESTIGATOR STUDY PLAN - REQUIRED

feedback about what they found helpful or unhelpful and concrete suggestions for improving the intervention.

Aim 2 Pilot Feasibility RCT

After randomization and receipt of the training intervention, participants will contact the research team to schedule a study session in which they will engage in **three measures of outcome**:

- At the beginning of the study session, participants will complete a **ten-question multiple choice test** to assess their understanding and retention of intervention content. *The specific content of this test will be informed by our final training intervention, so will be submitted in a Modification prior to any RCT recruitment taking place.*
- A virtual informed consent simulation (≈ 1 hour). Zoom meetings will be created to reflect a virtual healthcare appointment including informed consent procedures (for participating healthcare providers). When participants are sent the Zoom link for their study session, the bottom of the email will include subtle contact information for “Interpreter Services.” This contact information will include the direct email address to our research team’s ASL interpreters in order to facilitate bringing an interpreter onto the Zoom call (if the participant so chooses). The Zoom simulation will be recorded using the in-platform recording feature. At the start of the Zoom meeting, participating healthcare providers and the standardized patient will have access to virtual tools, such as autogenerated captioning and the chat box function. The standardized patient will be masked to study condition.
 - **Team Rating of Simulation.** Team members who participate in the simulation and team members who review the recording (at least three in total) will complete an evaluation following the simulation. This evaluation will assess the participant’s performance conducting culturally-appropriate informed consent using validated scales of provider cultural competence (*Healthcare Provider Cultural Competency*), communication skill (*Ask, Understand, Remember Assessment*), and ability to build trust with the standardized patient/participant (*Wake Forest Physician Trust Scale*).
 - **Self-Rating of Simulation** (≈ 15 minutes). Immediately after the simulation, participants will complete a self-assessment using the validated scales described above to rate their conduct of culturally-appropriate informed consent in the simulation and are also asked to provide feedback on the study experience.

11. PROCEDURES INVOLVED*

Aim 1a Focus Groups

Across six months, we will recruit 48 participants to eight focus groups – two groups with hearing researchers, research coordinators, and research project directors; two with hearing healthcare providers and medical/nursing students; two with Deaf research personnel, healthcare providers; and two with Deaf community members. We will continue data collection until we reach the point of saturation - i.e., the point in the research process when no new information is discovered in data analysis. As such, we propose to add up to two additional focus groups if needed to reach the saturation point: (1) medical interpreters (including hearing and Deaf

INVESTIGATOR STUDY PLAN - REQUIRED

interpreters) and (2) other miscellaneous stakeholders (e.g., family members of Deaf individuals, people connected to both hearing and Deaf communities).

Focus groups will be held on Zoom and will run for 2 hours. [name] will facilitate the groups with hearing participants in English; [name] and [name] will co-facilitate groups with Deaf participants in ASL. Participants will view the *Sign Here* prototype film (view here: <https://www.youtube.com/watch?v=HtPGWljNVeg&feature=youtu.be>) and, using prompts informed by the Deaf Community Advisors, the facilitators will elicit feedback about what participants found helpful or unhelpful and concrete suggestions for improving the intervention. The focus groups will be recorded on Zoom and stored on a secure, password-protected server. Participant compensation will be a \$150 gift card.

Aim 2 Pilot Feasibility RCT

In Year 2, our team will conduct a two-arm pilot RCT to test the feasibility and acceptability of our new *Sign Here* training intervention, as well as evaluate preliminary efficacy via medical simulation. We will recruit 80 local healthcare providers and medical/nursing students from UMCMS/UMMMC, as well as from our colleagues' collaborating institutions – Brown University and Harvard University.

REDCap will be configured to **randomly assign** an intervention condition to each participant: (1) the new *Sign Here* training film, or (2) an “intervention as usual” control. As outlined below, prior to the study session, participants randomized to the **experimental condition** will be asked to view the *Sign Here* training film; participants randomized to **intervention as usual** will be provided with the standard NIH guidance on how to communicate informed consent to Deaf or hard-of-hearing individuals.

Recruitment materials will include a link to our **eligibility screening** survey in REDCap. Eligible individuals will be immediately directed to a second survey page that includes **eConsent** information. At the time of eConsent, REDCap will randomize the participant. Our team’s Research Liaison will then send the participant an email with the intervention appropriate to their study condition and instructions for the participant to contact our team to schedule their study session once they have completed their intervention. When scheduling for the study session, participants will be asked to come prepared with an informed consent form that they are comfortable using for the simulation and will receive a link from the study coordinator for a virtual session using UMCMS Zoom accounts. Additionally, as noted above, when participants are sent the Zoom link for their study session, the bottom of the email will include subtle contact information for “Interpreter Services.” This contact information will include the direct email address to our research team’s ASL interpreters in order to facilitate bringing an interpreter onto the Zoom call (if the participant so chooses).

Participants will be scheduled for a 1.5-hour study session on Zoom. Then, during the study session, the participant will engage in a simulated virtual encounter in which they are asked to conduct informed consent with a Deaf standardized patient (i.e., portrayed by one of our Deaf Community Advisors). The PI and Co-Is will provide intensive training to the standardized patient, including supervised role-plays, to ensure that a realistic, consistent portrayal is

INVESTIGATOR STUDY PLAN - REQUIRED

achieved. At the end of participation, all participants will be compensated with a \$100 Visa gift card.

1. **Eligibility Screening.** Recruitment materials will include a link to our study's eligibility survey in REDCap. This survey will also query basic demographic characteristics, professional experience, amount of prior experience conducting informed consent, and perceived skill level for conducting informed consent procedures.
2. **Informed Consent.** For eligible participants, REDCap will immediately present a second page with informed consent information to participants via the eConsent platform.
3. **Intervention Conditions. (15 - 20 minutes).** Following eligibility screening and eConsent, REDCap will randomize participants. Our Research Liaison will then send an email to the participant with the intervention based on their assigned condition:
 - a. *Experimental condition.* Participants independently view the *Sign Here* training film.
 - b. *Intervention as usual condition.* Participants independently review a paper copy of the "NIH Guidelines on Communicating Informed Consent for Individuals who are Deaf or Hard-of-Hearing and Scientists."
4. **Scheduling Study Session.** Participants will be instructed to contact our team to schedule their study session once they have completed their intervention. When scheduling for the study session, participants will be asked to come prepared with an informed consent form that they are comfortable using for the simulation and will receive a link from the study coordinator for a virtual session using UMCMS Zoom accounts.
5. **Content Test (≈ 15 minutes).** Regardless of study condition, at the beginning of their scheduled study session, participants will complete a ten-question multiple choice test to assess their understanding and retention of intervention content.
6. **Informed Consent Simulation (≈ 1 hour).** Zoom meetings will be created to reflect a virtual healthcare appointment including informed consent procedures. When participants are sent the Zoom link for their study session, this email will also provide contact information for "Interpreter Services," as described above. The Zoom simulation will be recorded using the in-platform recording feature. At the start of the Zoom meeting, participating healthcare providers and the standardized patient will have access to virtual tools, such as auto generated captioning and the chat box function. The standardized patient will be masked to study condition.
7. **Team Rating of Simulation.** Team members who participate in the simulation and team members who review the recording (at least three in total) will complete an evaluation following the simulation. This evaluation will assess the participant's performance conducting culturally-appropriate informed consent using validated scales of provider cultural competence (*Healthcare Provider Cultural Competency*), communication skill (*Ask, Understand, Remember Assessment*), and ability to build trust with the standardized patient/participant (*Wake Forest Physician Trust Scale*).
8. **Self-Rating of Simulation (≈ 15 minutes).** Immediately after the simulation, participants will complete a self-assessment using the validated scales described above to rate their conduct of culturally-appropriate informed consent in the simulation and are also asked to provide feedback on the study experience.

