6. INCLUSION AND EXCLUSION CRITERIA*

Our proposed aims are to create a new *Sign Here* training film for hearing healthcare providers and to conduct a pilot randomized controlled trial (RCT) to test the feasibility, acceptability, and preliminary efficacy of the new intervention. Aim 1a and Aim 2 include human subjects components and will be described separately through each relevant section below.

Aim 1a Focus Groups

Across six months, we will recruit 48 participants to eight focus groups – two groups with hearing researchers, research coordinators, and research project directors; two with hearing healthcare providers and medical/nursing students; two with Deaf research personnel, healthcare providers; and two with Deaf community members. We will continue data collection until we reach the point of saturation - i.e., the point in the research process when no new information is discovered in data analysis. As such, we propose to add up to two additional focus groups if needed to reach the saturation point: (1) medical interpreters (including hearing and Deaf interpreters) and (2) other miscellaneous stakeholders (e.g., family members of Deaf individuals, people connected to both hearing and Deaf communities). **Inclusion criteria** for all participants are: (1) age 18+; and (2) current or recent engagement in informed consent for human subjects research or clinical care.

Aim 2 Pilot Feasibility RCT

In Year 2, our team will conduct a two-arm pilot RCT to test the feasibility and acceptability of our new training intervention, as well as evaluate preliminary efficacy via medical simulation. We will recruit 80 local healthcare providers and medical/nursing students from UMCMS/UMMMC, as well as from our colleagues' collaborating institutions – Brown

INVESTIGATOR STUDY PLAN - REQUIRED

University and Harvard University. **Inclusion criteria** are: (1) age 18+; (2) current or recent engagement in informed consent for clinical care; and, (3) access to an informed consent form that can be used for a simulated informed consent session (so the participant will be familiar with the content). We will also screen participants' self-reported level of experience with Deaf people, as we aim to recruit participants with (4) little-to-no prior experience interacting with Deaf people to reflect the most probable real-word encounter that a Deaf person would have when receiving healthcare services.

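### The consent form used in the simulation is not fixed before randomisation, so the arms could be rated on consent tasks of different difficulty

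*Combined protocol and SAP*

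**What the plan says.** Section 6 (Aim 2), criterion 3, makes it a condition of entry to have "access to an informed consent form that can be used for a simulated informed consent session". The reason given is "so the participant will be familiar with the content". Use of the participant's own form is therefore deliberate. The criterion does not ask which form it is.

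Section 11 (Aim 2) sets the order of events:

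- Allocation comes at consent: "At the time of eConsent, REDCap will randomize the participant".
- The research liaison then emails the film or the NIH guidance.
- Scheduling follows the training: "Participants will be instructed to contact our team to schedule their study session once they have completed their intervention".
- At scheduling (step 4), "participants will be asked to come prepared with an informed consent form that they are comfortable using for the simulation".

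The patient's side of the encounter is standardised. The standardized patient receives intensive training, "including supervised role-plays, to ensure that a realistic, consistent portrayal is" achieved. No corresponding step covers the form: the plan sets no common form, no limits on length or complexity, no collection at screening and no log of the form used.

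Sections 10 and 11 take the team ratings and the self-ratings of cultural competence, communication and trust from this one simulation. Section 13 compares them between arms by ANOVA, with no term for the form.

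**The concern.** The form sets the content of the consent task. A short consent for a routine procedure and a long consent with several treatment options are not equally hard to convey to a Deaf patient. Participants are providers and medical or nursing students from several institutions, so the forms could vary widely.

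Because the request comes after allocation and after the assigned material, the choice of form is open to influence by the arm. If it were influenced, part of any difference in ratings would reflect an easier or harder task rather than better conduct of the same task. Aim 2a in Section 4 names cultural competence, communication skill and ability to build trust as what is measured. The effect sizes in Section 13 are also meant to inform a multi-site trial, where a contrast mixing skill and task would be hard to interpret.

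If the choice is unrelated to arm, randomisation balances form difficulty in expectation. The cost is then extra variance, not bias.

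**Working it through.** **Plan's own figure.** Section 6: "We will recruit 80 local healthcare providers and medical/nursing students from UMCMS/UMMMC" and collaborating institutions. The plan gives no alpha, power, effect size, SD or dropout rate, so 80 cannot be reproduced. Nor does it state an allocation ratio; it says only that "REDCap will be configured to randomly assign an intervention condition to each participant". Assumed below: 40 per arm, two-sided alpha 0.05, normal approximation.

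**Order of events.** Screening (access to a form required) → eConsent and randomisation → material emailed → material completed → participant contacts the team → participant asked to bring a form. Nothing between the first step and the last identifies the form.

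**Scale.** The standard error of a standardised difference is √(2/40) = 0.224. The difference detectable with 80% power is (1.960 + 0.842) × 0.224 ≈ 0.63 SD.

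**(a) Form choice depends on arm.** Let g be the gain in rating from an easier form, in SD, and Δp the difference between arms in the share using it. Both are assumptions. The shift is b = g × Δp. With no skill effect at all, the rejection rate is 1 − Φ(1.96 − b/0.224) + Φ(−1.96 − b/0.224).

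| g (SD) | Δp | Shift b (SD) | Rejection rate at zero skill effect |
|---|---|---|---|
| 0.25 | 0.10 | 0.025 | 0.051 |
| 0.5 | 0.20 | 0.10 | 0.073 |
| 0.5 | 0.40 | 0.20 | 0.145 |
| 1.0 | 0.30 | 0.30 | 0.269 |

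The last row is 0.30/0.63 ≈ 0.48 of the detectable difference. The first row is negligible. The shift can favour either arm.

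**(b) Form choice unrelated to arm.** Let f be the share of score variance due to the form (assumed). A true effect of 0.63 in SD units of skill becomes 0.63 × √(1 − f) in SD units of the total score. The standard error relative to a task without form variance is 1/√(1 − f). The SD of chance imbalance between arms is √(2f/40).

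| f | Relative standard error | Power for 0.63 skill SD | SD of chance imbalance |
|---|---|---|---|
| 0 | 1.00 | 0.80 | 0 |
| 0.10 | 1.05 | 0.76 | 0.07 |
| 0.20 | 1.12 | 0.71 | 0.10 |
| 0.30 | 1.20 | 0.65 | 0.12 |

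Naming the form before randomisation addresses (a). It leaves (b) in the main ANOVA, because participants still use different forms.

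**The case against.** A reader might infer that the form is in fact picked after randomisation and that the film steers participants to easier forms, so that the efficacy contrast is biased. The documents do not support that.

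- Criterion 3 already requires access to a suitable form at screening. Many participants may have one in mind and keep to it. The documents say when the form is requested, not when it is chosen.
- The control arm is not naive. It reads NIH guidance on communicating consent to Deaf or hard-of-hearing people, so both arms know the topic before the request. A difference in form choice is possible, but nothing documents it and it could run either way.
- The analysis by assigned arm estimates a valid total effect of assignment. Section 5 counts jargon-heavy written forms as part of the problem, so choosing a plainer form could be seen as part of what the film achieves. Wanting skill isolated on a comparable task is partly a choice of estimand.
- Nothing in the documents shows that these ratings depend on the length or type of form.
- Sessions are video-recorded and reviewed, so the procedure discussed could probably be coded afterwards. The plan is silent on whether the team sees the form beforehand; that silence does not show that it does not.

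All of this stands, and it limits the point to a safeguard. What it does not answer is that the plan leaves open a choice the arm could influence, with no provision to detect it. The familiarity reason supports using the participant's own form. It does not require leaving the form unidentified until after training.

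**Conclusion.** The point holds as a gap in the design that is cheap to close, not as a demonstrated bias. The form can be chosen or changed after allocation, and no step logs it. The arms could therefore be rated on tasks of different difficulty without the team knowing.

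The size is not derivable from the documents. Across the assumed inputs it runs from nothing of consequence to a shift of about half the detectable difference, and every one of those figures rests on assumed values of g, Δp and f and on 40 per arm. If form choice did differ by arm, the ANOVA would still describe the effect of being assigned the film but could not be read as skill alone. The feasibility and acceptability outcomes do not depend on the argument.

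A reader might also infer that the fix recovers the 5–20% excess standard error in (b). It does not do so in the main comparison.

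**What to change.** Keep the participant's own familiar form, and identify it before allocation.

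1. Add a text field to the REDCap eligibility survey in which the participant names the form: procedure or treatment, and approximate length. No upload is needed.
2. State in Section 11, step 4, that this form is to be used in the session, and record any session in which a different one was used.
3. Report form type by arm.
4. In Section 13, add a sensitivity analysis of the efficacy comparison adjusted for the form type named before randomisation. The form actually used should not be the covariate, because it may itself be affected by the arm.

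The cost is one survey field, a sentence in step 4 and one extra analysis. Section 10 already foresees a Modification before trial recruitment for the content test; if that is still to be submitted, this change can go with it. The downsides are slightly more effort at screening, in a pilot where enrolment is itself an outcome, and a few participants who may later need to bring a different form.

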12. DATA AND SPECIMEN BANKING*

INVESTIGATOR STUDY PLAN - REQUIRED

N/A

13. DATA ANALYSIS AND MANAGEMENT*

Aim 1a Focus Groups

Video data will be uploaded into *ATLAS.ti*, where it can be coded directly in the source language (i.e., spoken English or ASL) without need for translation or transcription.^{34,35} Data will be analyzed using an inductive approach with two major techniques: (1) content analysis, in which the number of similar responses are tallied and described; and, (2) a summary of the answers to the questions outlined by Casey,⁴² including: *What is really important? Are there any comments said only once but deserve to be noted? What ideas will be especially useful for intervention?* Data will be coded collaboratively and simultaneously by all members of the research team, with conflicting points of view further discussed and resolved among the team.

Across six months, informed by focus group data and our Deaf Community Advisors, we will perform film editing on the *Sign Here* prototype and, as needed, additional film production to create two refined, final versions of *Sign Here* – one for research personnel and one for healthcare providers. To produce these products, our team will work with [name], a filmmaker with extensive experience producing ASL films and the director of the *Sign Here* prototype. The intervention development team will include Deaf and signing researchers, clinicians, actors, and ASL consultants to maintain a high level of Deaf community engagement.

Aim 2 Pilot Feasibility RCT

Data will be entered into Research Electronic Data Capture (REDCap), a secure web-based application with real-time data entry validation (e.g., data types, range checks).^{44,45} Drs. [name] and [name] will customize the database to track recruitment, intervention delivery, and feasibility and efficacy outcomes. Data will be exported to *SAS* for quantitative analyses and *ATLAS.ti* for qualitative analyses. Data quality will be examined before analysis, including examination of missing data, assessment of distributional assumptions, and identification of outliers.

Feasibility and acceptability outcomes include recruitment, enrollment, and retention rates; intervention fidelity; participant satisfaction; and feasibility of assessment. We will record the number of individuals screened versus enrolled and reasons for ineligibility or non-participation. We will record the number and reasons for failure to complete the interventions, and any discrepancies between RCT arms. [name] will review all intervention sessions for fidelity. Intervention engagement and participant satisfaction will be ascertained from the measures described above and discussion during the debriefing. Qualitative data regarding participant engagement and satisfaction will be analyzed using the procedures described above.

To evaluate **preliminary efficacy outcomes**, we will first examine whether there are any baseline differences between the experimental group and the intervention-as-usual group using chi-square (categorical variables) or analysis of variance (ANOVA; continuous variables). We

INVESTIGATOR STUDY PLAN - REQUIRED

will then use ANOVA to compare differences in mean scores at post-intervention between the two groups on team member ratings and self-ratings of provider cultural competence, communication skill, and ability to build trust. Effect sizes will be estimated for the primary outcomes. To calculate effect size, the difference between the two group means of an outcome will be divided by either their pooled standard deviation or by the standard deviation of the control group.

We will also evaluate future **implementation potential** via online training platforms by evaluating the ten content test questions which could potentially accompany the *Sign Here* film as part of an online training module. We will assess whether intervention condition (dichotomous variable) predicts content test scores (continuous variable), and whether these content test scores are strongly related to real-world change on performance measures of provider cultural competence, communication skill, and ability to build trust (continuous variables). To examine the effect of the intervention on content test scores, we will compare differences in mean scores at follow-up between the two groups using ANOVA. Effect size will be estimated for content test scores. Pearson correlation analysis will be conducted to examine the strength of associations of content test scores with provider cultural competence, communication skill, and ability to build trust during the simulation encounter.

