27. PROVISIONS TO PROTECT THE PRIVACY INTERESTS OF SUBJECTS

During the informed consent process, participants will be informed that they have the right to refrain from answering any questions. It will be emphasized that any information provided by the participant is completely voluntary and that they can leave the study at any time if they choose.

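### Cheap improvement: Section 13 compares unadjusted post-intervention means, although prior consent experience and perceived consent skill are recorded before randomisation; prespecified adjustment may improve precision, by an amount the documents do not settle.

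*Combined protocol and SAP*

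**What the plan says.** All references are to the combined protocol and SAP.

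- **Ratings.** Section 13 (Aim 2, preliminary efficacy) states that the team "will then use ANOVA to compare differences in mean scores at post-intervention between the two groups on team member ratings and self-ratings" of cultural competence, communication skill and trust-building. The effect size is the difference in group means divided by the pooled or the control-group standard deviation.
- **Content test.** In the same section, under implementation potential: "we will compare differences in mean scores at follow-up between the two groups using ANOVA".
- **Use of baseline data.** Before the ANOVA, "we will first examine whether there are any baseline differences between the experimental group and the intervention-as-usual group", by chi-square or ANOVA. No consequence of the result is stated.
- **Items available.** Section 11, step 1, lists what the eligibility survey asks besides eligibility: "basic demographic characteristics, professional experience, amount of prior experience conducting informed consent, and perceived skill level for conducting informed consent procedures".
- **Timing.** Section 11 puts eConsent after the survey and says "At the time of eConsent, REDCap will randomize the participant". Both consent-related items therefore precede allocation.
- **Raters.** Sections 10 and 11 have at least three team members rate each simulation. Section 13 does not say how their ratings are combined.

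**The concern.** Two items that could bear on how well someone conducts a consent discussion are to be collected before randomisation, and the efficacy analysis leaves them out. If they predict the outcome, a model that includes them estimates the arm difference more precisely from the same participants. That precision includes removing the part of the error that comes from chance imbalance in these items.

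The baseline tests also lead nowhere. If one shows a difference, the plan does not say whether to adjust or for what, so the choice would be made after seeing the data.

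At stake is the width of the interval around each effect estimate. Section 4 says the results will inform the design of a multi-site RCT, and Section 13 says effect sizes will be estimated. The stake is modest: adjustment alone will not make a pilot effect size reliable for planning.

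**Working it through.** The plan gives no power, alpha, standard deviation or target effect, so there is no figure of its own to reproduce.

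**Inputs.** From the documents: 80 randomised to two arms (Section 4). Assumed: 1:1 allocation with all 80 analysed (40 per arm), one score per participant, outcome SD of 1, two-sided 95% intervals, and a joint correlation R between the items and the outcome ranging from 0 to 0.5.

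**Formula.** With N analysed and p covariate terms, the ratio of adjusted to unadjusted standard error is

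sqrt[(1 - R²) × (N - 3)/(N - p - 3)].

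For N = 80 and p = 2, the second factor is 77/75 = 1.0267.

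| R | SE ratio | Change in SE | 95% CI half-width (SD) |
|---|---|---|---|
| unadjusted | 1 | – | 0.445 |
| 0 | 1.013 | +1.3% | 0.451 |
| 0.1 | 1.008 | +0.8% | 0.449 |
| 0.3 | 0.967 | -3.3% | 0.430 |
| 0.5 | 0.877 | -12.3% | 0.391 |

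The half-width is t(0.975, df) × sqrt(2/40) × ratio, with df = 78 unadjusted and 76 adjusted. Break-even is R = sqrt(1 - 75/77) = 0.16. A simulation of 4,000 trials per setting gave variance ratios of 1.035, 0.934 and 0.778 at R of 0, 0.3 and 0.5; the formula gives 1.027, 0.934 and 0.770.

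**Size in participants.** 80/0.934 = 86 at R = 0.3 and 80/0.770 = 104 at R = 0.5: the unadjusted trial that would give about the same precision.

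**Coding.** If the two items became six category terms, the factor is 77/71. The SE changes by +4.1%, +3.6%, -0.7% and -9.8% at the same four values of R, and break-even rises to sqrt(1 - 71/77) = 0.28.

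**Attrition.** With 70 analysed (35 per arm) and two terms, the factor is 67/65. The changes are +1.5%, +1.0%, -3.1% and -12.1%, with break-even at 0.17.

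**Missing items, if there are any.** Dropping k participants gives, relative to the unadjusted analysis of 80, sqrt[80/(80 - k)] × the ratio at N = 80 - k. At R = 0.3 this is 0.999 for k = 5 and 1.035 for k = 10, so the gain is lost. With overall-mean imputation and 5–10% of each item missing completely at random (simulated, 20,000 trials per setting), the gain stays at about 3% for R = 0.3 and 11% for R = 0.5, without visible bias.

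**Chance imbalance.** With 40 per arm, a standardised covariate difference has standard error sqrt(2/40) = 0.224. A difference of at least 0.30 SD in a given covariate therefore occurs in about 18% of randomisations. If that covariate correlates r with the rating, it shifts the raw difference by 0.30r, or 0.03 to 0.15 SD for r of 0.1 to 0.5. This error is already part of the variance in the table.

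**The case against.** The strongest reply is that nothing is broken. Under randomisation the planned ANOVA is unbiased, the trial is a pilot about feasibility and acceptability as well as preliminary efficacy, and the benefit depends on an R that nobody has measured. At R = 0.3 the half-width moves by only 0.445 - 0.430 = 0.015 SD, and below R of about 0.16 adjustment does slight harm. All of that stands. It limits the point to an optional improvement; it does not remove the case for one whose worst outcome, with single-term coding, is an SE about 1% larger.

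R may well be low for some outcomes. The two items concern consent in general, whereas the participants sought have "little-to-no prior experience interacting with Deaf people" (Section 6), and the content test is meant "to assess their understanding and retention of intervention content" (Section 10). Perceived skill and self-rating at least share a source, the participant's own judgement. The gain is therefore likely to be smaller for masked team ratings and the content test. This is a judgement; the documents give no data on it.

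One can also ask why these two items and not the others in the survey. They are the two specific to conducting consent, which is what the simulation scores. That makes them plausible predictors, not proven ones.

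Two stronger readings are tempting and are not supported:

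- *Screening items can be skipped, so baseline data will be missing.* A reader might infer this from Section 27, where "participants will be informed that they have the right to refrain from answering any questions". That notice is given during the consent process, after the screening survey has been answered. The documents do not say whether screening items can be skipped, so the missing-data figures above are hypothetical.
- *Protection against chance imbalance is a second benefit on top of precision.* It is not. The shift from imbalance is part of the variance that adjustment removes, and counting both would count one benefit twice.

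**Conclusion.** The point holds as a low-priority, low-cost improvement, with medium confidence. Section 13 names no covariate for any Aim 2 comparison, and two relevant items are to be collected before allocation. Adjustment may improve precision: about 3% in SE at R = 0.3 and 12% at R = 0.5, against a loss of about 1% at R = 0. These figures rest on 40 analysed per arm, one score per participant and single-term coding. The value of R, and hence the sign of the effect, is unknown.

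A reader might infer that the planned analysis is wrong or biased, or that adjustment is certain to help. The documents support neither: the ANOVA is a valid comparison of randomised groups, and no correlation is given from which a gain could be established.

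**What to change.** In Section 13, prespecify for each team rating, each self-rating and the content test:

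1. A linear model with one score per participant on arm, perceived consent skill and prior informed-consent experience. For team ratings, use the mean across raters: an ordinary linear model on rater-level rows would treat correlated ratings as independent.
2. Each item entered as a single linear or ordinal term. The items and their scoring are fixed before outcome data are seen and are not chosen from the baseline tests.
3. The adjusted difference with its 95% CI, standardised by the unadjusted pooled SD so that effect sizes stay comparable.
4. The unadjusted ANOVA as a sensitivity analysis.
5. If any baseline item is missing, imputation by the overall mean ignoring arm, so that no participant with an outcome is dropped.

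**Cost.** Plan wording only, with no new data; but the wording must include a scoring rule, because Section 11 gives no response format for the items. The statistical price is an SE about 1% larger if the items are unrelated to the outcome (1.5% with 70 analysed), and about 4% larger if they are coded as six category terms.
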